# 5.5. Recruitment Procedures, Identification index cases and selection of secondary cases

Suspected malaria cases attending local health services (rural health center and sub-centers) or village malaria workers (VMW) will be tested with a cRDT as in routine practice. All cases parasitologically confirmed by cRDT will be treated according to national guidelines, and asked for informed consent to participate in the study. If the patient gives informed consent, the VMW or basic health staffs will promptly notify the study team, using mobile phone. Additionally, finger prick blood will be collected from the index case to test with hsRDT, and on dry blood spot (DBS) for later PCR analyses.

The study team will conduct the investigation visit at the residence of the index case within 3 days, and the index cases will be interviewed using a standard case investigation form (Annex 1). All members of the index case's household will be invited to participate in the study and

interviewed using the participants' questionnaires (Annex 2) to assess a history of malaria in previous year, travel information, and utilization of malaria prevention measures. The nearest ten households around the index case's household will be identified by using household listing. All members, including temporary visitors, of these ten households will be invited to participate in the study and interviewed using the participants' questionnaires (Annex 2), tested with cRDT and hsRDT, and a DBS will be collected for subsequent analysis. If the index case reports traveling to or working in the forest or other risk areas, co-travelers or co-workers will be also recruited in the study, when feasible.

Study participants who tested positive on cRDT or hsRDT will be treated according to national guidelines, in compliance with WHO recommendations and NMCP policies, which call for treatment of any RDT-positive infection. Although the diagnostic performance of hsRDT is under investigation, there is enough evidence that cRDT fails to detect low density infections, therefore treatment of hsRDT-positive malaria is conservative and ethically justifiable.

PCR results will not be available immediately, and there are no recommendations for retrospective malaria treatment based on ultrasensitive testing. Those who are ill but found to be negative on RDTs will be provided with information to seek further care and referral to an appropriate medical professional will be made. Study team will be equipped with basic medical supplies and provide as much care as possible.

## 5.6. Seeking Informed Consent/Assent from potential participants

Prior to the study data and sample collection, preliminary discussion meetings will be organized with all partners involved in the research (NMCP, VBDC Rakhine, DMR, Defeat Malaria partners, local authorities and community leaders) to explain the nature and scope of the study, and prompt their active collaboration. Community outreach activities will be conducted to ensure the community response and study participation. Study time line will be disseminated to the targeted communities in a locally appropriate manner.

The principles of research ethics in the current edition of the Declaration of Helsinki will be applied, and protocol-specified procedures will be initiated only after obtaining informed consent. The written consent documents will embody the elements of informed consent as described in the current edition of the Declaration of Helsinki, will adhere to the ICH Harmonized Tripartite Guideline for Good Clinical Practice and 45CFR46 and 21CFR50, and will also comply with applicable Myanmar regulations. The oral consent process will be consistent with 45CFR46.§46.117, 21CFR50.27 and ICH E6 (R1) Section 4.8.

Information about the study will be given to prospective participants, in a simple lay language both in Myanmar and Rakhine, in both oral and written forms whenever possible. Independent witnesses will be used to attest that illiterate potential participants have understood the contents of the informed consent document.

The UMB investigators and staff will closely work with the NMCP and other relevant local research staff at the study sites, providing training, and re-training if necessary, in Protection of human subjects, Good Clinical Practice, and responsible conducts of research to assure study information and informed consent procedures meet requirements of the community, sponsor and all relevant ethic review oversight committees. UMB investigators have published detailed descriptions of the processes that have been used to obtain community "permission to enter" and individual informed consent [42]. We consider informed consent to be a dynamic, ongoing

process, with continuous availability of investigators to answer any questions that arise in the course of the study and to ensure that participants and their parents/guardians understand study procedures. Even though subject participation will be brief for this study, these same principles will be followed.

Since the vast majority of study participants' parents/guardians do not use telephones, fax or mail, contact information is provided in terms of local physicians who can be visited directly and who can themselves reach the investigators directly or by telephone or fax.

In Myanmar, individuals who are at least 18 years old are considered adults and will provide consent for themselves; children 6 months to  $\leq$ 7 years of age are too young to provide assent; however, written consent will be provided by their guardian; children 8 to  $\leq$ 12 years of age will provide verbal assent, in addition to written consent provided by their guardian; children 13 to  $\leq$ 17 years of age will provide written assent, in addition to written consent provided by their guardian. In rural Myanmar guardians need not necessarily be the child's parent(s); Any close relative including aunts, uncles, grandparents, adult siblings etc. who accompany the child to the clinic may serve as the guardian for the sake of providing informed consent. This may include neighbors or village elders in the case of orphans.

## 5.7. Data and Blood Sample Collection

Participant will be given a unique study identification number which, instead of the participant's name or other personal identification, will be used for his/her case record forms, other study related documents and for labelling the study samples. This will minimize a potential loss of confidentiality for the participant.

A trained study personnel will clean with antiseptic, and prick the tip of the participant's finger (or the heel if and when appropriate for children 6–12 months old) using a lancet, and collect 5-7 drops of blood (a quarter of teaspoon). Two to three drops will be used to check for malaria by cRDT and hsRDT, and 3-4 drops will be collected on to filter papers for malaria PCR testing. The filter paper will be placed at the prick site on the finger to absorb the blood. For infants 6 months to one years of age, a heel prick might be more appropriate.

The PCR analysis will be carried out at the DMR in Yangon, with technical assistance and quality management from the University of Maryland. Additional molecular, antigen and antibody-based testing for malaria may be conducted depending availability of funding. The DBS, packed in individual plastic bags with desiccant, will be appropriately stored at Defeat Malaria's field office in Ann Township and sent to DMR in Yangon every 2-3 weeks.

# 6. Sample Management and Laboratory Evaluation

# 6.1. Specimen Collection, Preparation, Handling and Shipping

DBS specimens will be collected using standard methods (see

http://www.wwarn.org/learning/procedures/dbs-sample-collection-and-transportation). DBS samples will be labeled with participant unique ID. No names and other personal identifiers will be recorded. After collection, DBS will be air dried and stored in zip-lock plastic bags with desiccant at each site (see Appendix B: Molecular Testing for Malaria Standard Operating Procedures DBS Sample Collection and Transportation) at +4 °C, -20 °C or room temperature in a cool, dry, dark location.

## 6.2. PCR assay from dried blood spot

DNA will be extracted dried blood spots using a validated new extraction method developed by our group (Zainabadi et al. "A dried blood spot based ultrasensitive detection method for asymptomatic malaria" Oral presentation at the 57the annual meeting of American Society of Tropical medicine and Hygiene, November 2016). As much of the molecular analyses as possible will be done at the Advanced Molecular Research Center of the Department of Medical Research, under the Myanmar Ministry of Health. Extracted DNA will be subjected to ultra-sensitive qPCR using well-established techniques that currently have a lower limit of detection of 22 parasites/mL (9). PCR will be done in Myanmar with some duplicate samples analyzed at the University of Maryland for quality control purposes.

Future studies of parasite DNA derived from samples may be conducted without restriction. *No other studies on any topics beyond what is described in this protocol and consent/assent forms or on human DNA will be done unless specific permission for additional studies is obtained from the relevant IRBs.* Study participants will have the right to withdraw their permission for further use of their samples at any time during and after the study.

Samples will be batched and shipped periodically to the DMR laboratory and/or the laboratories at the University of Maryland in Baltimore or CDC-Atlanta. DBS specimens will be shipped at room temperature and desiccant will be replaced upon receipt. Specimen receipt will be logged using a system designed at UMB using the Freezer works program. The laboratory contact at DMR is [name] [name], E-mail: [contact]. The laboratory contact at UMB is the lab supervisor [name] E-mail: [contact].

# 7. Statistical consideration and Data Management

## 7.1. Power calculation with available sample size

The primary limitation is the size of population that needs to be screened since malaria burden may be low in the study sites, and associated financial costs and logistical difficulties.

The primary endpoint of this proposed study is the prevalence of secondary malaria cases identified by hsRDT in comparison with usPCR prevalence. Based on our current data on prevalence of *P. falcipaum* in 2016, and logistical and financial considerations, the recruitment of 50 index cases is feasible in a given study period. This will give us a total of 1980 individuals for testing of secondary cases in ACD, assuming the average household member of 4.5, 11 households for each index case (counting the household of the index case) and a refusal rate of 20% (4.5 persons/HH x 11 HH x 50 index cases x 0.80=1980).

We conservatively estimate that hsRDT will detect 20% of usPCR+ *P. falciparum* infections (i.e., sensitivity of hsRDT=0.2 using usPCR as gold standard). We expect very few recently treated individuals to be enrolled in the study, so that hsRDT should only rarely give a positive result when usPCR does not. Hence we assume that the specificity of hsRDT is 0.995. Table 1 shows estimated statistical power that can be achieved with the proposed sample size of 1980 for comparing the prevalence by hsRDT and the prevalence by usPCR, at different malaria prevalence by usPCR and different sensitivity of hsRDT, using a two-sided McNemar test with a Type I error of 5%. (PASS version 11. NCSS, LLC. Kaysville, Utah, USA)

As shown in Table 1, if the sensitivity of hsRDT is 0.2 and the specificity of hsRDT is 0.995, a sample size of 1980 subjects achieves at least 92% power to detect the difference in prevalence between hsRDT and usPCR when the malaria prevalence is 2% or higher. If the sensitivity of hsRDT is 0.5 (see the last four columns of Table 1), a sample size of 1980 subjects achieves at least 86% power when the malaria prevalence is 3% or higher. If the prevalence of malaria is higher, the performance of hsRDT will be better with a higher sensitivity and positive predictive value.

 Table 1. Statistical power expected with proposed sample size of 1980 at different malaria

| prevalence and different sensitivity of hsRDT (assumed sensitivity of 20% or 50% and |
|--|
| specificity 99.5%)   |

| Prevalence
by usPCR | Sensitivity
of hsRDT | Specificity of hsRDT | Estimated
prevalence
by hsRDT | Power | Sensitivity
of hsRDT | Specificity
of hsRDT | Estimated
prevalence
by hsRDT | Power |
|------------------------|-------------------------|----------------------|-------------------------------------|-------|-------------------------|-------------------------|-------------------------------------|-------|
| 0.02                   | 0.2                     | 0.995                | 0.009                               | 0.92  | 0.5                     | 0.995                   | 0.015                               | 0.45  |
| 0.03                   | 0.2                     | 0.995                | 0.011                               | >0.99 | 0.5                     | 0.995                   | 0.020                               | 0.86  |
| 0.06                   | 0.2                     | 0.995                | 0.017                               | >0.99 | 0.5                     | 0.995                   | 0.035                               | >0.99 |
| 0.12                   | 0.2                     | 0.995                | 0.029                               | >0.99 | 0.5                     | 0.995                   | 0.065                               | >0.99 |

Table 2 below shows changes in the power of the study, if the specificity of hsRDT is 0.95 (increased false positive by hsRDT), while the sensitivity of hsRDT and baseline true prevalence remain the same.

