New "ultrasensitive" PCR-based tests, with a lower limit of detection 16–22 parasites/mL [4, 7-9], have recently found unexpectedly high rates of subclinical malaria in Southeast Asia. These infections are missed by standard diagnostics such as microscopy or conventional RDT which have a lower limit of detection about 100 parasites/uL. Though the PCR is adequately sensitive to detect these low-density infections, its utility is quite severely limited by its complexity, requirement for advanced skills and infrastructure, cost, and by the fact that it is not a point-of-care test. Today's malaria elimination toolkit essentially consists of prompt diagnosis and treatment using rapid diagnostic tests (RDTs) and artemisinin-based combination treatments (ACTs), vector control methods, and surveillance using RDTs and/or microscopy. The available diagnostic tests are inadequate to detect these low-density malaria infections, and new tools are urgently needed.

Three studies, a survey, and a systematic review assessing the role, appropriateness and benefits of the ACD strategy, both proactive and reactive, in low transmission settings have been recently conducted in Cambodia, Indonesia, Thailand, India and other Asian-Pacific countries [10-12]. The data clearly indicated that the ACD strategy needs to be optimized based on the local context, and on evidence for the adoption of improved methods. The need for better, cheaper and more accurate diagnostic tools, with an increased capacity to detect low density malaria infections, was highlighted in recent literature.

To fill this critical gap, a new hsRDT that has a potential to be at least 10- to 20-fold more sensitive for detecting low density infections than standard cRDT was developed (Standard Diagnostics Bioline Inc. Gyeonggi-do, Republic of Korea), and is now under field evaluation in several malaria endemic countries. This test is similar in design to cRDT, using a handheld point-of-care laminar flow test to detect low levels of the *P. falciparum* antigen Histidine Rich Protein 2 (HRP2), which is also one of the detection targets of cRDT. Initial prototype testing of the new hsRDT designed to detect the *P. falciparum*-specific antigen *HRP2* in a format

similar to the current cRDT resulted in a limit of detection (LOD) of *HRP2* of about 80 pg/mL compared to cRDTs with a LOD of 800–1000 pg/mL (personal communication, [name], Diagnostics & Global Health, Bill & Melinda Gates Foundation).

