We propose to evaluate the role of this new hsRDT in the setting of reactive case detection (RCD) in specified townships where malaria prevalence has been steadily declining. Our primary goal is to assess whether or not this new hsRDT performs significantly better than cRDT in identifying subclinical submicroscopic infection, and to subsequently evaluate if hsRDT can be used for effective ACD in Myanmar. The proposed study may shed light on the development of national standard operating procedures (SOPs) for ACD as recommended by the NMCP. The development of these SOPs are ongoing, and our study may provide timely and relevant contribution for their development, particularly assessing the detection accuracy and utility of the new hsRDTs when used as a screening tool in the RCD strategy. Additional useful information can be obtained on the applicability, cost, and operational challenges faced during the field implementation.

The proposed study also addresses PMI elimination or priority to "Evaluate the utility and scalability of more sensitive diagnostic tools (e.g. highly-sensitive RDTs, PCR, etc.) in an elimination context, including their utility for reactive or proactive case detection." It will also contribute to current PMI research activities comparing RCD with RDTs to focal Mass Drug Administration (MDA) planned for Madagascar and Ethiopia. The Madagascar study will also include the hsRDT in their RCD arm. If the test of this hsRDT in detecting additional malaria infections around index cases shows good field performance, further trials can be planned in Myanmar to evaluate its role in malaria elimination.

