#### **Specific objectives:**

1. To evaluate the prevalence of malaria infections identified by the new hsRDT in comparison with that detected by cRDT and PCR

Outcomes: malaria test positivity rate by cRDT, hsRDT and PCR, respectively

2. To assess the diagnostic performance characteristics of hsRDT *versus* cRDT, using PCR as gold standard, in the detection of *P.falciparum* infections

Outcomes: Sensitivity, specificity, positive and negative predictive values of hsRDT and cRDT

3. To evaluate correlation of detection capability between cRDT and hsRDT

Outcomes: Correlation of test positivity rate by the three different study tests

4. To identify risk factors associated with malaria infection, including but not limited to, socio-demographic factors and travel history related with malaria index cases

Outcome: Relative risk of malaria in association with different risk factors identified

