# 7.2. Analytical Plan

All data will be double-entered into Epi-Info and any discrepancies will be reviewed against the paper forms. All analyses will be conducted using Stata/SE (version 14), using data from the participant interviews and the three parasitological tests.

The malaria test positivity rate will be calculated as a proportion of samples tested that are positive using cRDT, hsRDT and PCR, respectively. Corresponding 95% confidence intervals (CIs) will be computed using exact method. A 2x2 table method will be used to calculate the sensitivity, specificity, positive and negative predictive values of hsRDT (and cRDT) and their corresponding 95% CIs using PCR as gold standard. The malaria prevalence by each test (e.g., the rate of malaria test positive) will be compared between each two tests (hsRDT vs PCR; cRDT vs PCR; hsRDT vs cRDT) using McNemar test. All statistical tests will be performed with a two-sided significance level of 0.05.

Descriptive analysis will be conducted to assess socio-demographics characteristics. Univariate analysis will include t-test and non-parametric methods for continuous variables and chi-square test for comparison of categorical variables. Multi-level regression models will be developed to examine risk factors significantly associated with malaria infections, accounting for clustering by index case.

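### The stated goal is hsRDT against cRDT, but the primary endpoint and all power figures concern hsRDT against usPCR positivity, and no paired accuracy comparison of the two RDTs is planned or powered

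*Combined protocol and SAP*

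**What the plan says.** Section 3.1 of the protocol states: "Our primary goal is to assess whether or not this new hsRDT performs significantly better than cRDT in identifying subclinical submicroscopic infection". Objective 2 in section 4 also sets the two RDTs against each other: "To assess the diagnostic performance characteristics of hsRDT *versus* cRDT, using PCR as gold standard, in the detection of *P.falciparum* infections".

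Section 7.1 names a different comparison: "The primary endpoint of this proposed study is the prevalence of secondary malaria cases identified by hsRDT in comparison with usPCR prevalence". Tables 1 and 2 give McNemar power for that comparison only. No sensitivity or specificity is assumed for cRDT anywhere. Objective 1 does include the comparison with PCR ("To evaluate the prevalence of malaria infections identified by the new hsRDT in comparison with that detected by cRDT and PCR"), and the four objectives are not ranked.

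Section 7.2 plans two relevant analyses. Sensitivity, specificity and predictive values are computed for each RDT against PCR, each with its own 95% confidence interval. Positivity in all participants "will be compared between each two tests (hsRDT vs PCR; cRDT vs PCR; hsRDT vs cRDT) using McNemar test".

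**The concern.** The comparison that is named primary and powered is not the one the study says it wants to settle. A significant primary result would establish that hsRDT and PCR positivity differ, which the sample size section already assumes by setting hsRDT sensitivity at 0.2 or 0.5. A non-significant result could arise because many missed infections are balanced by false positives.

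The one planned test of hsRDT against cRDT counts every positive as a detection, including positives that PCR does not confirm. A less specific hsRDT could therefore appear to find more malaria. No interval or test is specified for the difference between the RDTs within PCR-positives or within PCR-negatives, although every participant has all three tests. The results are meant to inform national procedures for active case detection, so the main conclusion should not rest on comparing two sets of unpaired intervals.

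**Working it through.** **Inputs from section 7.1.** N = 4.5 × 11 × 50 × 0.80 = 1980; two-sided McNemar test at 5%; hsRDT sensitivity (Se) 0.2 or 0.5; specificity (Sp) 0.995 (Table 1) or 0.95 (Table 2); usPCR prevalence p = 2, 3, 6 or 12%.

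**Formulas.** For hsRDT against PCR, the discordant cells are missed infections, p(1 − Se), and false positives, (1 − p)(1 − Sp). hsRDT positivity is p·Se + (1 − p)(1 − Sp). Power is by binomial enumeration of the discordant pairs, given as exact / uncorrected asymptotic.

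**Step 1: the plan's own figures (Sp 0.995).**
- p = 2%, Se 0.2: 1980 × 0.016 = 31.7 missed, 1980 × 0.0049 = 9.7 false positives; power 0.92/0.94 (printed 0.92).
- p = 2%, Se 0.5: 19.8 missed, 9.7 false positives; power 0.39/0.47, normal approximation 0.46 (printed 0.45).
- p = 3%, Se 0.5: power 0.88/0.91, continuity-corrected normal approximation 0.86 (printed 0.86).

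The printed powers are therefore for hsRDT against usPCR positivity. At 2% prevalence the better test has the lower power. That direction is not general: at p = 6% and Sp 0.95, power is about 0.05 at Se 0.2 and 0.76/0.78 at Se 0.5.

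**Step 2: the same accuracy gives three verdicts.** Table 2 is meant to show what happens "if the specificity of hsRDT is 0.95 (increased false positive by hsRDT), while the sensitivity of hsRDT and baseline true prevalence remain the same". With Se 0.2 and Sp 0.95:

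| Prevalence | hsRDT positivity | False positives | Missed | Power | Reading |
|---|---|---|---|---|---|
| 2% | 5.3% | 97 | 32 of 40 | >0.99 | hsRDT above PCR |
| 6% | 5.9% | 93 | 95 of 119 | 0.04/0.05 | no difference |
| 12% | 6.8% | 87 | 190 of 238 | >0.99 | hsRDT below PCR |

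These values are not visible in Table 2. The left half of that table repeats Table 1's prevalences (0.009, 0.011, 0.017, 0.029), and its power column (0.053, 0.055, 0.059, 0.068) holds what are in fact the hsRDT prevalences at Sp 0.95.

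**Step 3: the planned hsRDT-versus-cRDT positivity test with no gain in sensitivity.** Se is 0.2 for both, p = 2%, and cRDT specificity is assumed to be 0.995. With independent false positives the discordant cells are b = (1 − p)(1 − Sp_h)Sp_c and c = (1 − p)(1 − Sp_c)Sp_h. With cRDT false positives nested within hsRDT's, b = (1 − p)(Sp_c − Sp_h) and c = 0. If the RDTs are independent among PCR-positives, add p × 0.16 to both cells. Exact rejection probability, from independence to full agreement among PCR-positives:

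| hsRDT specificity | Independent false positives | Nested false positives |
|---|---|---|
| 0.99 | 0.27–0.36 | 0.46–0.92 |
| 0.985 | 0.75–0.86 | 0.93 to >0.99 |
| 0.95 | >0.99 | >0.99 |

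**Step 4: power for the stated goal.** PCR-positives number 1980p ≈ 40, 59, 119 and 238. Nested results have b = Se_h − Se_c and c = 0. Independent results have b = Se_h(1 − Se_c) and c = Se_c(1 − Se_h). cRDT sensitivities are assumed. Exact McNemar power, independent / nested:

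| hsRDT vs cRDT sensitivity | 2% | 3% | 6% | 12% |
|---|---|---|---|---|
| 0.20 vs 0.15 | 0.05 / 0.01 | 0.07 / 0.07 | 0.13 / 0.55 | 0.26 / 0.98 |
| 0.20 vs 0.10 | 0.15 / 0.21 | 0.24 / 0.55 | 0.50 / 0.98 | 0.84 / >0.99 |
| 0.20 vs 0.05 | 0.39 / 0.57 | 0.61 / 0.89 | 0.93 / >0.99 | >0.99 / >0.99 |
| 0.50 vs 0.25 | 0.55 / 0.96 | 0.74 / >0.99 | 0.97 / >0.99 | >0.99 / >0.99 |

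The McNemar version matters: for 0.20 vs 0.10 nested, the uncorrected asymptotic test gives 0.58 and 0.85 at 2% and 3%. Substantial overlap between the RDTs is plausible, since section 3.1 says of the HRP2 antigen "which is also one of the detection targets of cRDT". None of these figures allows for clustering by index case.

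**The case against.** The strongest reply is that the plan is not silent on the two RDTs. Section 7.2 has a paired McNemar test for them and accuracy estimates with intervals for each. In the 6% scenario above, the report would show sensitivity near 0.20 beside the non-significant p-value, so the missed infections would be visible. This stands, and it narrows the gap to the absence of an interval or test for the paired difference within PCR strata, together with the absence of power for it.

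The reversal in step 2 needs Sp 0.95; at 0.995, misses exceed false positives in every Table 1 cell. Step 3 needs hsRDT to be less specific than cRDT. With both specificities at 0.995, equal sensitivity and independent errors, rejection is only about 0.03. With equal specificity and nested errors, the planned test has nearly the power of the restricted one (0.21 and 0.55 at 2% and 3% for 0.20 vs 0.10). These points are correct. But 0.95 is the protocol's own alternative, and the trial exists to learn the specificity, so the analysis should not depend on its being high.

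Power for the stated goal could also be good: an assumed cRDT sensitivity of 0.02, nested, gives 0.75 and 0.97 at 2% and 3%. Sharing HRP2 makes overlap likely without proving full nesting. The documents therefore cannot show that 1980 is too few.

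Finally, the section 3.1 goal concerns subclinical submicroscopic infection, whereas an analysis of all PCR-positive contacts is wider, and no microscopy of contacts is planned. That population does match objective 2, but the wording should be aligned. The paired data could be analysed later in any case, though that choice would no longer be prespecified.

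**Conclusion.** The concern holds and should be fixed before analysis. The mismatch is plain from the text, and the power figures in steps 1 and 2 use only the protocol's own inputs. The primary comparison can give opposite answers for a test of unchanged accuracy, and the planned positivity test between the RDTs can be significant through loss of specificity alone; the size of that second effect rests on the assumed cRDT specificity, the assumed hsRDT values of 0.99 and 0.985, and the agreement between tests. The finding is that power for the stated goal was never assessed, not that it is inadequate. The step 4 spread shows that Table 1's 0.92 cannot stand in for it.

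**What to change.** In sections 7.1 and 7.2, make the primary analysis the paired difference in sensitivity, hsRDT minus cRDT, among usPCR *P. falciparum*-positive contacts, with a 95% confidence interval and a McNemar test restricted to those contacts. Report the paired difference in specificity among PCR-negative contacts beside it. Keep the overall-positivity comparisons as secondary or descriptive, and align the goal in section 3.1 with this population.

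Replace the headline power with power for this comparison over the same prevalence grid, with a stated range of cRDT sensitivity and between-test agreement. Name the McNemar version and say how clustering by index case is handled.

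The cost is a protocol amendment, review by the ethics bodies listed in section 5.1, revised analysis wording and a new power table. No new samples or tests are needed and N stays at its feasibility limit. The drawback is that stated power at 2–3% prevalence may look less favourable.

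### The primary McNemar comparison of hsRDT and PCR prevalence tests only whether missed infections equal false positives, so it cannot show whether hsRDT finds the infected people

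*Combined protocol and SAP*

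**What the plan says.** Section 7.1 defines the primary endpoint: "The primary endpoint of this proposed study is the prevalence of secondary malaria cases identified by hsRDT in comparison with usPCR prevalence". Power is calculated "using a two-sided McNemar test with a Type I error of 5" per cent. The main inputs are low sensitivity ("i.e., sensitivity of hsRDT=0.2 using usPCR as gold standard") and high specificity ("Hence we assume that the specificity of hsRDT is 0.995"). The conclusion is that "a sample size of 1980 subjects achieves at least 92% power" "when the malaria prevalence is 2% or higher". Table 2 is a stress case that asks what happens "if the specificity of hsRDT is 0.95 (increased false positive by hsRDT), while the sensitivity of hsRDT and baseline true prevalence remain the same".

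Section 7.2 plans McNemar tests of test positivity for all three pairs of tests. It also plans the accuracy measures: "A 2x2 table method will be used to calculate the sensitivity, specificity, positive and negative predictive values of hsRDT", and of cRDT, with 95% confidence intervals and PCR as reference. In section 4 these are the outcomes of specific objective 2, and they are not named as primary. Section 3.1 gives the primary goal as whether hsRDT does better than cRDT. No section gives a success rule, an equivalence margin or a reading of a non-significant primary result.

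**The concern.** McNemar's test on two prevalences uses only the discordant pairs: PCR-positive/hsRDT-negative (missed infections) and PCR-negative/hsRDT-positive (false positives). It asks whether the two counts are equal. It does not use the number of infections that hsRDT found, so it does not ask whether the right people were identified.

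Neither outcome therefore answers the diagnostic question. Rejection says that hsRDT and PCR count differently, which a planning sensitivity of 0.2 already implies. Non-rejection may mean that both errors are small, that two large errors offset each other, or that there were too few discordant pairs. The sample size is justified on this comparison alone, while the quantities that a malaria programme would use have no stated precision.

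**Working it through.** **Inputs (section 7.1, Tables 1 and 2).** N = 1980; two-sided alpha 0.05; prevalence p = 0.02, 0.03, 0.06, 0.12; sensitivity Se = 0.2 or 0.5; specificity Sp = 0.995 or 0.95.

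**Formulas.** Missed: b = p(1 − Se). False positive: c = (1 − p)(1 − Sp). hsRDT prevalence = p·Se + c. Power ≈ Φ{[|b − c|√N − 1.96√(b + c)] / √[b + c − (b − c)²]}, plus the opposite tail when b is close to c.

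**Step 1: the plan's own figure.** p = 0.02, Se = 0.2, Sp = 0.995:
- b = 0.0160 and c = 0.98 × 0.005 = 0.0049.
- Power = Φ[(0.494 − 0.283)/0.144] = Φ(1.46) = 0.928. Enumeration of the exact McNemar test gives 0.923.
- The stated 0.92 is reproduced. At Se = 0.5 the formula gives 0.46 against the stated 0.45.
- Table 1's 0.86 (p = 0.03, Se = 0.5) computes as 0.89. This does not affect the point.

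**Step 2: all eight scenarios with Se = 0.2.**

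| p | Sp | Missed | False positive | hsRDT prevalence | Power |
|---|---|---|---|---|---|
| 0.02 | 0.995 | 31.7 | 9.7 | 0.009 | 0.93 |
| 0.03 | 0.995 | 47.5 | 9.6 | 0.011 | >0.99 |
| 0.06 | 0.995 | 95.0 | 9.3 | 0.017 | >0.99 |
| 0.12 | 0.995 | 190.1 | 8.7 | 0.028 | >0.99 |
| 0.02 | 0.95 | 31.7 | 97.0 | 0.053 | >0.99 |
| 0.03 | 0.95 | 47.5 | 96.0 | 0.0545 | 0.98 |
| 0.06 | 0.95 | 95.0 | 93.1 | 0.059 | 0.05 |
| 0.12 | 0.95 | 190.1 | 87.1 | 0.068 | >0.99 |

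Seven of the eight have power of about 0.93 or more. One cancels.

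**Step 3: the cancelling case.** p = 0.06, Se = 0.2, Sp = 0.95:
- PCR-positive: 0.06 × 1980 = 118.8, of which 23.8 are found and 95.0 missed.
- False positives: 0.94 × 0.05 × 1980 = 93.1.
- hsRDT-positive: 23.8 + 93.1, or 116.8 before rounding; 116.8/1980 = 0.059 against 0.060 by PCR.
- Rejection: Φ(−1.82) + Φ(−2.10) = 0.035 + 0.018 = 0.052; exact test 0.044. This is about the alpha level.
- 80% of infections are missed, and 93.1/116.8 = 80% of hsRDT positives are PCR-negative.

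**Step 4: where cancellation falls.** b = c when p = (1 − Sp)/[(1 − Se) + (1 − Sp)]. For Se = 0.2:
- Sp = 0.995: 0.005/0.805 = 0.6%; power below 50% for prevalence of about 0.2% to 1.3%.
- Sp = 0.98 (an assumed intermediate value, not in the plan): 0.02/0.82 = 2.4%; power below 50% for about 1.5% to 3.6%.
- Sp = 0.95: 0.05/0.85 = 5.9%; power below 50% for about 4.4% to 7.6%.

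**Step 5: Table 2 as printed.** For the row in Step 3 (left half), Table 2 prints hsRDT prevalence 0.017 and power 0.059. The left-half prevalence column (0.009, 0.011, 0.017, 0.029) repeats Table 1. The left-half power column (0.053, 0.055, 0.059, 0.068) equals the recalculated prevalences in Step 2. The columns appear misaligned. The prevalence of 0.059 used here is therefore a recalculation from the plan's inputs, not the plan's printed value.

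**The case against.** The strongest reply has four parts.

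- **Cancellation is not typical.** At the base specificity, which the plan justifies by expecting few recently treated participants, a test with sensitivity 0.2 is declared different at every tabulated prevalence. Specificity 0.95 is a stress case, and only its 6% row cancels. This stands. It limits how often the problem would show, but it does not make the McNemar test a test of accuracy.
- **Accuracy is already planned.** In the cancelling case the 2x2 table would show sensitivity and positive predictive value both near 20%. This also stands, and confines the fault to the primary endpoint and the power basis.
- **No closeness rule exists.** A reader might infer that the plan rates hsRDT by how near its prevalence comes to PCR, or that a null result will be reported as equivalence. The documents say neither. They set a two-sided difference test and do not say how to read it.
- **Falling power is ordinary.** A reader might take the drop from 0.92 to 0.45 as sensitivity rises from 0.2 to 0.5 to mean that better tests are penalised. Power falls because the true difference shrinks, and power is not a rating of the test.

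A further tempting reading is that the near-5% powers in the left half of Table 2 show cancellation at every prevalence. They do not: recalculated, three of those four powers are about 0.98 or more.

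**Conclusion.** The concern holds in limited form. The primary comparison tests whether missed infections equal false positives and cannot establish whether hsRDT identifies infected people. A significant result adds little to what the plan assumes, and a non-significant one cannot be read as agreement with PCR.

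The extreme case (95 missed, 93 false positives, about 5% rejection) arises in one of the eight tabulated scenarios with sensitivity 0.2. The documents do not support the wider inference that a test missing 80% of infections would generally look equal to PCR, or that the study as a whole could not detect such a failure. The left half of Table 2 needs correction in any case.

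The calculations take PCR as error-free, use the plan's own inputs and N = 1980, and ignore clustering by index case, for which the documents give no intraclass correlation.

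**What to change.** In sections 7.1 and 7.2:

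1. Make hsRDT sensitivity and specificity for P. falciparum against PCR the primary measures, as a pair with 95% confidence intervals. Report the same pair for cRDT and a paired comparison of the two tests, so that the goal in section 3.1 is addressed.
2. Keep test positivity as descriptive objective 1, shown with both discordant counts against PCR. State that a non-significant prevalence difference is not agreement with PCR.
3. Replace the power statement with expected precision. At 3% prevalence, 0.03 × 1980 ≈ 59 participants are PCR-positive and 1921 PCR-negative. Exact 95% intervals, before any clustering allowance, are: sensitivity 12/59, 0.11 to 0.33; sensitivity 30/59, 0.37 to 0.64; specificity 1911/1921, 0.990 to 0.998.
4. Correct the left half of Table 2 if the table is kept.

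The change is to wording and needs no new participants or data, because both RDTs and PCR are already done on each participant and the accuracy measures are already planned. The cost is that the quoted 92% power gives way to fairly wide sensitivity intervals at low prevalence.
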